**I. BACKGROUND AND SIGNIFICANCE**

Abdominal aortic aneurysm (AAA) is a significant medical problem, with a high mortality rate, accounting for approximately 150,000 hospital admissions per year. AAA is the 10th leading cause of death in Caucasian men, ages 65 - 74 years, and has accounted for nearly 16,000 deaths overall. Necropsy studies from the United States and Europe suggest an overall prevalence for AAA of 2-4% for men and 1-2% for women. Population based screening studies demonstrate a prevalence of approximately 9% in men and 2% in women. It has been demonstrated that the prevalence of AAA increases with increasing age, with an increased prevalence in males compared to females. Noninvasive screening in the elderly population has led to an overall increased incidence of asymptomatic AAA. Currently, 35,000 to 40,000 aneurysms are treated surgically in the United States. Once AAA formation has commenced, aneurysms will continue to grow at a variable rate, until they ultimately rupture. AAA rupture is associated with very high morbidity and mortality. Perioperative mortality rates of approximately 45% have been reported for open AAA repair in the United States since the late 1980s. Approximately 60% of patients with ruptured AAA die before reaching the hospital, and emergency open surgical repair carries a mortality rate of 35-70%. The incidence of AAA rupture continues to increase despite aggressive attempts to screen at-risk populations. Improvements in early aneurysm detection and surveillance are necessary to decrease the incidence of AAA rupture and associated mortality.

It is believed that AAA rupture occurs when the aortic wall stress exceeds the tensile strength of the degenerated AAA wall. Finite element analysis (FEA) may be utilized to implement biomechanical principles in an effort to assess AAA expansion and/or rupture risk. Efforts have been made to include intraluminal thrombus (ILT) and the anisotropic AAA tissue behavior into the computer models of AAAs. AAA rupture occurs when the stress acting on the AAA wall exceeds its strength; therefore, the prediction of AAA rupture must include wall stress and strength distributions. Considering this, rupture potential index (RPI) is defined as the ratio of the acting wall stress to the wall strength, and the maximum RPI for AAA represents its rupture risk. Comparing peak stresses and strains using anisotropic and isotropic constitutive relations, we have demonstrated significant increases in peak stress when using the anisotropic relationship. Considering ruptured AAA patients (N=8) and non-ruptured AAA patients (N=4), we have demonstrated a significant decrease in AAA wall strength of those AAAs that went on to rupture. The differences in RPI values did not reach statistical significance, when comparing ruptured and non-ruptured AAAs; however, our initial data suggests that peak RPI may serve as a better predictor of AAA rupture than maximum diameter or peak wall stress alone.

It is hypothesized that the final event leading to aortic rupture involves the degradation of collagen within the media, extending out through the adventitia. This occurs through a catalytic process induced by inflammatory cells in the aortic wall. Macrophages and neutrophils are a major source

of key enzymes at play, particularly serine proteases and matrix metalloproteinases, and are believed to play a critical role in this tissue degradation. Inflammation of the vascular wall related to phagocytic macrophage activity can be demonstrated by increased uptake of 2-deoxy-2-[F]fluoro-D-glucose (F-FDG) PET in the arterial wall. Accordingly, F-FDG PET has been used to assess AAA wall inflammation, and increased F-FDG uptake has been identified in symptomatic AAAs (pain on palpation of AAA) and with rapid aortic enlargement. Considering symptomatic AAA patients (N=3), Reeps *et al.* demonstrated significantly increased F-FDG AAA uptake that correlated with greater macrophage populations on AAA wall histology, as well as higher MMP9 expression and decreased collagen fiber content, when tissue was taken at the time of repair. In a follow-up manuscript, Reeps *et al.* demonstrated the ability to discriminate between symptomatic (N=5) and asymptomatic (N=18) AAA patients on the basis of F-FDG uptake. They then correlated this increased F-FDG uptake with aortic wall macrophage infiltration and MMP9 expression. We have reviewed F-FDG PET scans for AAA patients at a single institution compared with those of atherosclerotic, non-aneurysmal aortas and demonstrated significantly greater global F-FDG uptake by AAAs. Utilizing the porcine pancreatic elastase (PPE) exposure model in rats stimulated to rupture with  $\beta$ -aminopropionitrile (BAPN) exposure, we have demonstrated the ability of F-FDG microPET to identify metabolically active sites in a pre-rupture state that ultimately rupture.

Translocator protein (TSPO), formerly referred to as peripheral benzodiazepine receptor, is an 18-kDa outer mitochondrial protein highly expressed in phagocytic inflammatory cells, such as macrophages in the periphery and macrophage-like microglial cells in the central nervous system. It has been demonstrated that other inflammatory cells including neutrophils, B cells, natural killer, as well as CD4- and CD8-positive cells express TSPO to varying degrees. The TSPO radioligand C-PBR28 ([methyl-C]N-acetyl-N-(2-methoxybenzyl)-2-phenoxy-5-pyridinamine) has been used for neuroimaging with primates and humans, as well as imaging lung injury in humans. Other TSPO radioligands, including C-PK1195, have been utilized to evaluate macrophage presence and behavior in rodent and human carotid plaques.

We have previously demonstrated the utility of F-FDG and C-PBR28 to study inflammation associated with the PPE model of AAA development in rats, thereby verifying similar F-FDG imaging characteristics in this model compared to humans. In conjunction with increased TSPO gene expression and protein expression in AAA, this data supports the potential role of F-FDG and TSPO radioligands for the assessment of aortic wall inflammation during the development of aortic aneurysms in patients. Based on macrophage uptake and autoradiographic findings, as well as the natural history of AAA rupture, we are seeking to explore the uptake and distribution of TSPO radiotracers compared to F-FDG and the potential of C-PBR28 for the prediction of AAA expansion and/or rupture. This is the first study to assess the use of C-PBR28 to confirm the work we have performed in rat models of AAA expansion and rupture. The goal of this project at this point is not to change current subject management, but we plan to establish the groundwork that will serve as a basis for a larger scale study in the future.

## **II. SPECIFIC AIMS**

The aim of this project is to assess the ability of three different imaging techniques to determine

abdominal aortic aneurysm (AAA) rupture risk individually and in concert. Currently, the primary factor considered for risk of human AAA rupture is aortic diameter; however, it is well documented that small AAAs (<5cm) rupture, while many large AAAs (>8cm) are incidentally discovered. Thus, there is no absolute diameter threshold at which AAAs rupture. Approximately 60% of patients with ruptured AAA die before reaching the hospital, and emergency open surgical repair carries a mortality rate of 35-70%. This suggests that a new diagnostic modality must to be developed to reliably predict AAA rupture risk.

We will image subjects with atherosclerotic, non-aneurismal aortas as a control group. We will also image smaller, surveillance size (3.0-4.5cm) AAAs, AAAs that will undergo treatment (female >5.0cm, male >5.5cm), as well as rapidly expanding AAAs (>0.5cm over 6 months and/or >1.0cm over 12 months). The assessment of AAA wall structural integrity by FEA, generated utilizing CTA, will be studied in the context of increased metabolic activity and inflammation determined by F-FDG and C-PBR28 PET. We hypothesize that areas of increased F-FDG and C-PBR28 uptake will correlate; however, areas of more discrete, focal C-PBR28 uptake will correlate with areas of greatest RPI and decreased strength in the AAA wall, and this will be most pronounced in rapidly expanding AAAs. However, we also hypothesize that a fraction of smaller AAAs will exhibit a similar pattern, demonstrating areas of increased metabolic activity and inflammation that are at increased risk of expansion and/or rupture, independent of size or diameter.

**Aim 1.** Perform coregistered, FEA, as well as F-FDG and C-PBR28 PET of the infrarenal aorta using PET-CTA.

**Approach.** Consider a rapidly expanding AAA group that will demonstrate changes in the structural integrity and inflammatory cascade within the AAA wall validating a current approach to AAA treatment. Consider a surveillance group of AAA subjects that will demonstrate the ability of FEA as well as F-FDG and C-PBR28, to identify those subjects that are at increased risk of AAA expansion and/or rupture, independent of size.

**Aim 2.** Compare patterns of decreased aortic strength with patterns of increased stress and inflammation across three subject groups to determine the appropriateness of expanding these analyses to a larger group of clinically relevant subjects.

**Approach.** Utilizing evolving software to evaluate the same aortic volume across data sets, we will compare areas under greatest stress and lowest strength determined by FEA. Multiplanar and volumetric analyses of co-registered, FEA as well as F-FDG and C-PBR28 PET images will also be performed. With direct co-registration of the data sets for each subject, qualitative comparisons will be made regarding areas of F-FDG and C-PBR28 uptake, as well as stress, strength, and RPI.

### **III. SUBJECT SELECTION**

Twenty-four subjects will be recruited for this study. Six control subjects (three males and three females), will be considered. Control subjects will have known atherosclerosis by standard clinical criteria, without aneurysmal disease. Six subjects (three males and three females) with small AAAs

(diameter 3.0-4.5cm), six subjects (three males, AAA >5.5cm and three females, AAA >5.0cm) with AAAs that are indicated for treatment, and six subjects (three males and three females) with rapidly expanding AAAs (>0.5cm over 6 months and/or >1.0cm over 12 months) will be considered. During a clinical visit, the treating physician will introduce the study to each subject, and the study coordinator will provide a comprehensive description and materials to the subject.

Subjects 45 years of age or older will be considered and subjects from any at-risk populations (e.g.: cognitively impaired persons, prisoners) will not be included. A subject will not be eligible for inclusion if any exclusion criteria for PET-CTA apply. Any woman of childbearing age, who is planning to become pregnant, is breastfeeding, and/or suspects she may be pregnant, will not be enrolled in the study.

A subject will not be eligible for inclusion in this study if any of the following criteria apply:

- less than 45 years of age;
- pregnant or breastfeeding;
- any greater than normal potential for cardiac arrest;
- Renal disease – defined as eGFR < 60mg/ml/1.73m^2
- claustrophobic reactions and/or is unable to lie comfortably on a bed inside the scanner for 60 minutes as assessed by physical examination and medical history (e.g. back pain, arthritis);

A TSPO polymorphism has been previously demonstrated, and quantitative interpretations of signal can be confounded by interindividual variability in binding affinity. To avoid this confounder, we will perform Ala147Thr TSPO polymorphism genotyping as part of the screening process. Those subjects identified as mixed affinity or high affinity from the genetic testing results will continue with PET-CTA imaging. Those subjects who are identified as low affinity will be considered screen failures and will not have PET-CTA scanning performed.

Eligibility will be determined by a screening interview and review of the medical record. All subjects recruited for the study will be able to withdraw from the study at any time.

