## **VI. BIOSTATISTICAL ANALYSIS**

This is an exploratory (hypothesis generating) study. Subject Maximum transverse diameters, mean and peak wall stresses, mean and minimum wall strengths, and mean and peak RPI values will be compared between groups using a Students *t*-test, with  $P < 0.05$  indicating significance. Aortic wall  $^{11}\text{C}$ -PBR28 and  $^{18}\text{F}$ -FDG uptake will be considered in terms of standard uptake values (SUV) considering the infrarenal abdominal aorta from the crossing of the left renal vein to the iliac bifurcation. Voxel-wise SUV values over the AAA will be qualitatively assessed across subjects and groups. Maximum (SUVmax) and mean (SUVmean) values normalized to the blood pool and non-aneurysmal thoracic aorta will also be considered. SUVmax and SUVmean values associated with areas of focal uptake will also be considered and compared across subjects and groups using a Students *t*-test, with  $P < 0.05$  indicating significance. Multiplanar and volumetric analyses of coregistered FEA, with  $^{11}\text{C}$ -PBR28 and  $^{18}\text{F}$ -FDG PET images will also be performed. With direct coregistration of the data sets for each subject, qualitative comparisons will be made regarding areas of  $^{11}\text{C}$ -PBR28 and  $^{18}\text{F}$ -FDG uptake, stress, strength, and RPI. Quantitatively, correlations of each data set per subject will be determined.

There will be experimental and control group analysis by comparing subject demographics and aortic image measures. ANOVA with post hoc analyses will be performed to compare the groups.

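### High- and mixed-affinity TSPO subjects are pooled in the between-group 11C-PBR28 SUV tests with no genotype term, so the confounder that screening is meant to avoid is only partly removed

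*Combined protocol and SAP*

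**What the plan says.** Section III (Subject Selection) warns that "quantitative interpretations of signal can be confounded by interindividual variability in binding affinity" and continues: "To avoid this confounder, we will perform Ala147Thr TSPO polymorphism genotyping as part of the screening process". The rule that follows has two parts: "Those subjects identified as mixed affinity or high affinity from the genetic testing results will continue with PET-CTA imaging", and "Those subjects who are identified as low affinity will be considered screen failures and will not have PET-CTA scanning performed". Section V (Study Procedures, Subject Screening) repeats this rule. Three affinity classes are therefore recognised, one is excluded and two are imaged.

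Section VI (Biostatistical Analysis) describes the group comparison of uptake: "SUVmax and SUVmean values associated with areas of focal uptake will also be considered and compared across subjects and groups using a Students" t-test at the 0.05 level. It adds that "ANOVA with post hoc analyses will be performed to compare the groups". It also says that SUVmax and SUVmean "values normalized to the blood pool and non-aneurysmal thoracic aorta will also be considered", without presenting this as a correction for genotype. Neither test has a genotype factor or stratum. Recruitment is balanced on sex only (three men and three women per group). The Specific Data Variables list does not include genotype.

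**The concern.** The plan says it avoids the affinity confounder, but its rule removes one class and leaves the high-versus-mixed difference in the data. With six subjects per group, the share of high-affinity subjects will often differ between groups by chance. Any such difference moves the group mean 11C-PBR28 SUV for a reason unrelated to inflammation. Even with equal shares, mixing two classes adds within-group variance and makes a true difference harder to detect.

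The point is limited to between-group 11C-PBR28 SUV comparisons. 18F-FDG uptake and FEA measures are outside it. So are co-registration and correlations within one subject, because genotype is constant within a subject.

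At stake is what the study hands on. Section I presents it as groundwork for a larger study, and Aim 2 asks whether these analyses should be expanded. A blurred or spurious group difference in the new tracer bears directly on that decision.

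**Working it through.** **The plan's own figure.** The Power Calculation gives about 10 per group for power 0.80 at alpha 0.05, but no effect size or SD, so it can only be solved backwards. Two-sided, normal approximation: d = (1.960 + 0.842) × √(2/10) = 1.25 SD. The exact t calculation gives 1.325 SD. At the planned six per group, a two-sample t-test has power of about 0.54 for a 1.325 SD difference. The plan accepts being below its own required size, so it has little power to spare.

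**Inputs.** From the documents: four groups of six, alpha 0.05. Assumed, because the documents do not give them:
- share q of imaged subjects with high affinity: 50–70%;
- mixed-affinity SUV lower by e = 0–50%;
- within-genotype SD of log SUV: 0.25;
- true group difference: 1.8 SD, which gives about 80% power for a t-test at n = 6.

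**Chance imbalance.** If genotype is unrelated to group, each group's high-affinity count is Binomial(6, q). At q = 0.5 the difference between two counts behaves as Binomial(12, 0.5) − 6, so:
- P(differ by 2 or more) = 1 − (924 + 2×792)/4096 = 0.39;
- P(differ by 3 or more) = 1 − (924 + 2×792 + 2×495)/4096 = 0.15.

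At q = 0.7 these are 0.34 and 0.11. Across all six pairs, the chance that some pair differs by 2 or more is 0.76–0.81, and by 3 or more 0.37–0.46.

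**Lost power.** The genotype shift in SD units is g = −ln(1 − e)/0.25. Pooling raises the variance by the factor 1 + g²q(1 − q). At e = 30% and q = 0.6: g = 0.357/0.25 = 1.43, the factor is 1 + 2.04 × 0.24 = 1.49, and the 1.8 SD difference shrinks to 1.8/√1.49 = 1.48 SD. Simulated power at q = 0.6, for one contrast between two of the four groups:

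| Mixed-affinity SUV lower by | ANOVA contrast, no genotype (20 df) | With genotype term (19 df) | Two-sample t-test, no genotype (10 df) |
|---|---|---|---|
| 0% | 0.84 | 0.82 | 0.80 |
| 10% | 0.83 | 0.82 | 0.78 |
| 20% | 0.77 | 0.82 | 0.73 |
| 30% | 0.68 | 0.82 | 0.63 |
| 40% | 0.55 | 0.82 | 0.50 |
| 50% | 0.41 | 0.82 | 0.37 |

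Checks on the assumptions:
- Over q = 0.5–0.7, unadjusted contrast power is 0.77–0.79, 0.67–0.70, 0.54–0.58 and 0.40–0.45 at 20%, 30%, 40% and 50%.
- At a 30% effect it is 0.48, 0.75 and 0.80 for log SD 0.15, 0.35 and 0.50.
- If normalisation removes half the log effect, it is 0.83, 0.80, 0.75 and 0.69 at 20%, 30%, 40% and 50%.
- At the 1.325 SD implied by the plan, unadjusted versus adjusted power is 0.59 versus 0.56 at no effect and 0.52 versus 0.57 at 20%.

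**False positives.** Averaged over random genotype mixes, the null rejection rate is 0.05 with or without the term. Given a particular mix it is not. If two groups differ by exactly three of six, the mean difference is biased by (3/6)g. The unadjusted contrast then rejects a true null about 0.06, 0.09, 0.12, 0.16 and 0.18 of the time at 10%, 20%, 30%, 40% and 50% effects, against 0.05 with the term. At exactly two of six it stays near nominal (about 0.045–0.058). With no imbalance it falls from about 0.045 to 0.001 as the effect rises from 10% to 50%, because the extra variance makes the test too conservative.

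**The case against.** The strongest reply is that the size of the harm is assumed. The documents give no genotype share, no high-versus-mixed SUV difference and no SUV SD. Large losses need shifts of about 1.4 SD or more, and at effects of 10% or less adjustment gains nothing. This stands, and the result is conditional for that reason.

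The 1.8 SD difference is larger than the roughly 1.3 SD behind the plan's sample size. True, but at 1.325 SD the pattern is the same at a lower level.

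Adjusting a two-group test costs more than 2 points: at 1.325 SD and no genotype effect, power falls from 0.54–0.55 to 0.49–0.50. That also stands. It is why the term belongs in the four-group ANOVA the plan already names, with the 11C-PBR28 group contrasts taken from that model instead of from separate t-tests.

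Normalisation to blood pool and thoracic aorta may absorb part of the effect. If it removes half, little is lost up to 30%. The documents do not say how much it removes, and raw SUVs are compared as well.

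The commonest imbalance, two of six, barely changes the false-positive rate. Correct: misleading rejections need three or more of six. The power loss does not depend on imbalance.

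The correlations are described only as "Quantitatively, correlations of each data set per subject will be determined". Read as within-subject, they need no genotype term. If a correlation were computed across subjects with one value each, genotype would matter there too.

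Finally, the study is exploratory. It nevertheless sets P < 0.05 tests, and the remedy uses data already in hand.

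**Conclusion.** The concern holds and should be fixed. The omission is plain in the text: the plan names the confounder, removes one of three affinity classes, and pools the other two in the between-group 11C-PBR28 tests. Average type I error is not inflated. The consequences are lost power and a possibly misleading contrast when the realised mix is uneven.

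Their size depends on a genotype effect the documents do not give. Under the stated assumptions the loss against an adjusted model is nil at about 10% or less, 5 points at 20%, 14 points at 30% and 41 points at 50%. It is smaller if SUVs vary more within genotype or if normalisation removes much of the effect. Confidence is high that the term is missing; how much it matters in this study is uncertain.

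**What to change.** In Section VI:
- Add genotype (high versus mixed) as a factor in the between-group ANOVA or linear model for 11C-PBR28 SUVmax and SUVmean, raw and normalised. Take the post hoc group contrasts from that model. A log scale is optional.
- Add genotype to the Specific Data Variables, report genotype counts by group, and mark individual 11C-PBR28 values by genotype in plots.
- State that the per-subject correlations are computed within subjects. With that, they need no genotype term; nor do the FDG and FEA comparisons.

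In Section III, reword the claim that genotyping avoids the confounder: exclusion removes the low-affinity class, and the model handles the high-versus-mixed difference.

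The cost is wording plus 1 of 20 error degrees of freedom. If genotype has no effect, power is 0.82 instead of 0.84 under the assumptions above. No extra subjects, scans or tests are needed, because genotype is already determined at screening. Recording and reporting genotype is worth doing even if the effect proves small.

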#### **IV. SUBJECT ENROLLMENT**

Subjects scheduled for a vascular surgery clinic visit who fulfill the eligibility criteria will be identified through the patient appointment log.

The clinicians will introduce the study to the subject during a clinic visit and will obtain permission from the potential subject to be approached by study staff. Subjects will then be approached in person (ideally, and whenever possible) by a study coordinator to undergo consent and schedule the study. At this time, subjects will be informed that the PET-CTA scanning session will be performed on the BJH main campus.

The subjects will be informed about the PET-CTA scans, including that these scans will have no benefit or impact on their management as well as the risks associated with receiving Iopamidol, a regularly used CTA contrast agent, as well as F-FDG and C-PBR28, the two radiotracers being studied.

Informed consent will be obtained from the subjects by a member of the study team prior to obtaining the TSPO polymorphism genotyping blood sample and before the imaging session. The study team member obtaining consent will explain the purpose of the study and its potential benefits to society at large. The protocols for the scans will be explained in detail. Subjects will be informed about potential risks and benefits of PET-CTA and that the scans will have no benefit or impact on their management. Subjects will be informed that they may withdraw from the study at any time, for any reason. They will be informed that their refusal to participate in the study or choosing to terminate participation at any point will have no influence on their future care and treatment. Study subject information will be protected under HIPAA guidelines.

All subjects will receive a one-time \$200 remuneration following completion of the study required PET-CTA scans. All subjects will also be offered parking validation for BJH main campus parking.

